## **11.9 Handling of Data from Withdrawn Subjects**

All such subjects who have at least 1 diary entry will be included in the intent-to-treat analysis population.

## **11.10 Safety and Tolerability Analyses**

### **11.10.1 Compliance**

Compliance will be assessed by parental/legal guardians report on the daily diary. Compliance with study product will be defined as receipt of at least 70% of the expected doses. The proportion of patients who are compliant will be reported by treatment group. Treatment group differences in compliance will be assessed using a Cochran-Mantel-Haenszel test stratified by study site.

### **11.10.2 Adverse Events**

The number of patients with adverse events will be tabulated by treatment group. The number of patients experiencing each adverse event will also be summarized by severity and relationship to study drug. If an adverse event is reported more than once during the study period for a given patient, the greatest intensity will be presented in the tables. For summary tables, adverse events will be grouped by organ system. We will also track the duration of each reported adverse event. Diarrhea, a key and expected adverse event, will be defined as the occurrence of  $\geq 3$  watery stools in 1 day or 2 watery stools per day for 2 consecutive days, and will be tracked in the daily diary. The incidence of serious adverse events and study medication discontinuation due to adverse events will also be compared using Fisher's exact test. Data listings and narratives will be provided for patients discontinuing treatment due to adverse events and patients with serious adverse events.

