	
1) Proportion with adverse events (including emergence of bacterial resistance). 2) Proportion who are compliant with study product (took <math>\geq 70\%</math> of the doses).
 
Flow of patients: We will review each child's PRSS scores every morning and will contact parents/legal guardians of children whose PRSS scores are not improving at the expected rate (see definition of treatment failure above). These children will be seen by the study team and rescue medication will be prescribed, as clinically indicated and without breaking the blind, but they will be continued to be followed in the same way (electronic daily diary and routine end-of-study follow-up visit).
 
Statistical methods:
 
The primary efficacy analyses will be:
 
 
• To determine whether the effect of treatment differs in children with and without nasopharyngeal colonization with respiratory pathogens (i.e., we will test for interaction).
 
• To determine whether the effect of treatment differs in children with and without colored nasal discharge (i.e., we will test for interaction).
 
 
Generalized estimating equations will be used for these analyses. The primary analysis will be based on the intention-to-treat principle and will use two-sided tests. The variables chosen to define the subgroups were based on extensive preliminary data indicating likely heterogeneity of treatment effect in subpopulations defined by the presence/absence of these variables. This sample size will allow us to test these 2 hypotheses simultaneously.

Laboratory Tests:
	
A nasopharyngeal swab (or mid-turbinate nasal swab if a nasalpharyngeal swab is unable to be obtained) will be obtained at the baseline and final visit from all participants, when possible. We will use the presence of respiratory pathogens as one of the subgrouping variables. These swabs will be shipped to the Microbiology Lab at the Children's Hospital of Pittsburgh (CHP) on ice within 48 hours. According to the preliminary data presented, shipping of swabs does not adversely affect the ability to recover the respiratory pathogens being investigated. The Microbiology Lab will identify S. pneumoniae, H. influenzae, and M. catarrhalis using standard microbiological techniques.

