## 2.3 Potential Risks and Benefits

### 2.3.1 Potential Risks

- 1) Amoxicillin clavulanate potassium - The most common side effect of amoxicillin clavulanate is diarrhea. Diarrhea is reported by about one third to one half of children who take this medication. Infrequently, children may develop vomiting, nausea, diaper rash, or abdominal pain. Rarely, anaphylaxis (a severe allergic reaction) may occur. The use of antibiotics has been linked to the development of resistant bacteria, both in the child receiving antibiotics and in the community at large. Finally, there is a risk that the child will not respond to amoxicillin clavulanate, and thus require a different treatment. Most of the reported side effects of amoxicillin clavulanate are mild to moderate and resolve when the medication is stopped.
- 2) Placebo - There is a theoretical risk that children receiving placebo may be symptomatic for a longer period of time or have more complications than children receiving antibiotics. None of the studies to date, however, have borne this out. The largest study to date found no difference in the time-to-resolution of symptoms in children on antibiotics. Similarly, there is no evidence that immediate treatment with antibiotics is more effective at preventing complications of sinusitis. Most complications of sinusitis seem to occur in older children (who are not included in this study) and occur during the first few days of an upper respiratory tract infection (before sinusitis is usually diagnosed). Placebo contains no active medications and an allergic reaction is very rare.
- 3) Nasopharyngeal swab - The NP swab may cause minor transient discomfort.

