#### Tertiary

- To evaluate compliance with study product
- To assess adverse events associated with use of amoxicillin clavulanate, including the development of bacterial resistance
- To compare resource utilization according to treatment strategy

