### 3.2.3 Tertiary outcomes

#### Safety Outcomes

- 1) Adverse events - The proportions of children experiencing adverse events will be compared. We will also track the duration of each reported adverse event. This will include a comparison of the number of children at the follow-up visit who have resistance organisms. Diarrhea will be defined as the occurrence of  $\geq 3$  watery stools in 1 day or 2 watery stools per day for 2 consecutive days, and will be tracked in the daily diary.
- 2) Compliance - In the daily diary, we will ask parents/legal guardians to record whether they administered the doses of study product. Administration of  $\geq 70\%$  of the doses will be considered compliant.

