### **6.3 Modification of Study Intervention/Investigational Product for a Participant**

Children failing study product and children in whom study product is discontinued because of adverse events will be treated with clindamycin plus cefixime, amoxicillin-clavulanate potassium, or levofloxacin, or a similar antibiotic, as clinically indicated and without breaking the blind. The results of the NP culture may be used to guide therapy.

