## 9 ASSESSMENT OF SAFETY

### 9.1 Specification of Safety Parameters

We will track common and important adverse events linked with the study product [i.e., Protocol-Defined Diarrhea (PDD), generalized rash, and bacterial resistance], any adverse event, which requires more than minimal medical intervention (see below for definitions), and all serious adverse events.

Because the study product is approved for use for children with sinusitis, we will only track 1) common or important adverse events linked with the study product (PDD, generalized rash), 2) severe adverse event (AEs which require more than minimal medical intervention, Table 4, below), and 3) serious adverse events (see section 9.2.3). PDD will be defined by the occurrence of three or more watery stools in 1 day or two watery stools daily for at least 2 days.

The occurrence of these AEs will be recorded from the first study intervention, Day 1 (enrollment), through the end-of-study follow-up visit.

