### 11.3 Analysis Populations

#### 11.3.1 Intent-to-Treat Population (ITT)

The ITT population will consist of all eligible randomized children with at least 1 diary entry. This population will form the basis for the primary and secondary efficacy analyses of study data as well as for the safety analyses.

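### The by-arm safety comparison dilutes amoxicillin-clavulanate's own harm, because events and resistance arising after a rescue antibiotic stay with the assigned arm, and no supplementary pre-rescue analysis is planned

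*Combined protocol and SAP*

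**What the plan says.** The objective (Section 3.1, Tertiary, repeated in 11.2) is worded around the drug: "To assess adverse events associated with use of amoxicillin clavulanate, including the development of bacterial resistance".

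The analysis is worded around the assigned arm:

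- Section 11.10.2: "The number of patients with adverse events will be tabulated by treatment group".
- Section 11.3.1, on the ITT set: "This population will form the basis for the primary and secondary efficacy analyses of study data as well as for the safety analyses".
- Section 9.1, on the collection window: "The occurrence of these AEs will be recorded from the first study intervention, Day 1 (enrollment), through the end-of-study follow-up visit".
- Section 3.2.3, on resistance: "This will include a comparison of the number of children at the follow-up visit who have resistance organisms". Section 11.5 adds a tabulation of change from baseline to follow-up.

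On rescue, Section 6.3 says that children failing study product, or stopping it for an adverse event, "will be treated with clindamycin plus cefixime, amoxicillin-clavulanate potassium, or levofloxacin, or a similar antibiotic", with the blind kept. Sections 4 and 7.5 list the same options for children failing study product. The Protocol Summary says of rescued children "but they will be continued to be followed in the same way".

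Two further provisions bear on the point. Section 11.3.2 plans supportive per-protocol analyses, safety included, in children who took 70% of doses. Section 11.10.2 also summarizes events by relationship to study drug. No section separates events, or resistance results, by whether they came before or after a non-study antibiotic.

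**The concern.** A placebo child who fails, is given an open-label antibiotic and then develops protocol-defined diarrhea or a generalized rash is counted as a placebo child with an event. The same applies to a resistant organism found at the final visit. If the rescue drug is amoxicillin-clavulanate, an event caused by the very drug under study appears in the comparator column.

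There is ample time for this. Section 3.2.2 expects more than 90% of failures around Days 3 and 4. A child rescued on Day 4 is observed for another 8 days if seen on Day 12, or 14 days if seen on Day 18. The resistance comparison is more exposed still, since its only post-baseline culture comes after any rescue that has taken place.

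The trial asks for whom antibiotics are worth giving, and readers will set benefit in each subgroup against diarrhea and resistance. They are likely to read the by-arm difference as the drug's side-effect burden against no antibiotic. It is the burden against placebo with rescue available, and the plan does not say which of the two is meant.

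**Working it through.** The plan states no figure for this dilution, so there is none to reproduce. Its size can be sketched for diarrhea.

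**Inputs**

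- A, risk on amoxicillin-clavulanate: Section 2.3.1 says "Diarrhea is reported by about one third to one half of children who take this medication". Values used: 0.33, 0.40, 0.50.
- p0, risk without antibiotic: not in the documents; assumed 0.10 or 0.20.
- r_p, share of placebo children given a rescue antibiotic: not in the documents; assumed 0.15, 0.25 or 0.40.
- r_a, the same share in the antibiotic arm: assumed to be half of r_p, capped at 0.15. The cap is the 15% failure rate that Section 3.2.2 expects in that arm. Rescue is a clinical decision, so failure and rescue need not coincide.
- t, share of the drug's excess risk that a rescued child acquires: assumed 1.0, or 0.6 for shorter exposure.

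**Formulas**

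- Observed placebo risk = p0 + r_p × t × (A − p0).
- Observed active risk = A + r_a × t × (1 − A) × x, with x = 1 − (1 − A)/(1 − p0).
- Relative shrinkage of the risk difference reduces to t × [r_p − r_a × (1 − A)/(1 − p0)].

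**Worked example:** A = 0.40, p0 = 0.10, r_p = 0.25, r_a = 0.125, so x = 1 − 0.60/0.90 = 0.333. The undiluted difference is 30 points.

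- t = 1.0: placebo 0.10 + 0.25 × 0.30 = 0.175; active 0.40 + 0.125 × 0.60 × 0.333 = 0.425; difference 25 points.
- t = 0.6: placebo 0.10 + 0.25 × 0.6 × 0.30 = 0.145; active 0.40 + 0.125 × 0.6 × 0.60 × 0.333 = 0.415; difference 27 points.

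**Ends of the grid**

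- Smallest (A = 0.33, p0 = 0.20, r_p = 0.15, r_a = 0.075, t = 0.6): 0.6 × [0.15 − 0.075 × 0.67/0.80] = 0.052, or 5.2%.
- Largest (A = 0.50, p0 = 0.10, r_p = 0.40, r_a = 0.15, t = 1.0): 0.40 − 0.15 × 0.50/0.90 = 0.317, or 31.7%.

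**Check with other assumptions:** background diarrhea 5-20%, placebo rescue 30-45% against 15% in the antibiotic arm, and 25-100% of the excess risk acquired.

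- If rescue adds no events in the antibiotic arm, shrinkage is simply r_p × t: from 0.30 × 0.25 = 7.5% to 0.45 × 1.0 = 45%.
- If rescue adds events there too, shrinkage is about 4-37%.
- With 15% rescued in both arms, it is about 1-15% across the two variants. Under this model the difference shrinks even with equal rescue, because rescue produces fewer new cases among children who are already at higher risk.

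The direction is the same in every scenario tried; the size is not.

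**Do the two other provisions remove the dilution?**

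- Per-protocol set: it is defined by study-product doses, not by rescue. The documents do not say that study product stops at rescue, and a child rescued late can still reach 70%. Where rescue does lower dosing, exclusion depends on outcome.
- Relatedness summary: this is a blinded judgement (Section 9.2.1) that can assign an event to another cause, so some post-rescue events may be recorded as not related. It does not date events against the rescue antibiotic and does nothing for the resistance comparison.

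**The case against.** The strongest reply is that the by-arm table answers a legitimate question, and one that the protocol describes. Section 2.3.1 says placebo here is not the absence of treatment and likens the trial to immediate versus delayed prescribing. For that contrast, counting all events by assigned arm is correct and protected by randomization. This stands. A reader might infer that the safety comparison is invalid or biased in the antibiotic's favor; the documents do not support that. Post-rescue PRSS scores also stay in the efficacy analysis (Section 11.8 uses every day with data), so if rescue works, benefit is diluted as well. Benefit and harm are measured on the same footing.

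A reader might also infer that the by-arm table is the only safety analysis, or that a pre-rescue count should become the main one. Neither follows. The per-protocol and relatedness analyses exist, though they help only in part. Stopping the count at rescue is informative, since rescued children are those not improving. Nor can a split of follow-up resistance recover the pre-rescue state, because there is a single follow-up culture.

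The magnitude is also open to challenge. The placebo rescue rate, background diarrhea and risk on rescue drugs are all assumed, and the alternatives to amoxicillin-clavulanate may carry a different risk. The 33-50% is diarrhea as reported, while mild loose stools are not collected under Table 4, so the absolute points may be too large for protocol-defined diarrhea. The relative shrinkage depends on A only through (1 − A)/(1 − p0) and is less sensitive to this. In the worked example a clear harm difference of 25-27 points remains.

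What survives is narrower. The objective is worded about the drug, the main analysis is about the strategy, and nothing planned bridges the two.

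**Conclusion.** The point holds as a gap between objective and analysis. The by-arm ITT comparison is valid for immediate antibiotic versus placebo with rescue, and it dilutes the harm of amoxicillin-clavulanate itself. Under the stated assumptions the diarrhea risk difference is reduced by about 5-32%; the wider set of assumptions gives up to 45%. The documents give no placebo rescue rate, so neither the size nor the claim that placebo children will be rescued more often can be established from them. No size can be put on the resistance dilution. These are tertiary outcomes and the efficacy tests are unaffected, so this is an inexpensive improvement worth making before unblinding, not a flaw in the trial's main conclusions.

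**What to change.** - Keep the by-arm ITT table in Section 11.10.2 as the main safety comparison, and state that it estimates immediate antibiotic versus placebo with rescue.
- In 11.10.2, prespecify a supplementary by-arm analysis of protocol-defined diarrhea and generalized rash with onset from first dose to the first non-study systemic antibiotic, or to the end of follow-up if none is given. Use a rate per child-day or cumulative incidence, because follow-up before rescue may differ between arms, and name the choice in advance.
- In 11.5, add a descriptive tabulation of follow-up resistance by arm and by receipt of any non-study antibiotic.
- Confirm that the start date of each non-study antibiotic is an eCRF field. Adverse event start dates are recorded (9.2.1) and diarrhea is tracked in the daily diary (3.2.3). For antibiotics, the text specifies receipt on Days 1-11 (3.2.2), a parent interview at the final visit (6.6) and type and duration of medication (11.10.3), but no start date. Medication collection at an interim visit is optional (7.5).

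The cost is a few tables and possibly one date field. The downside is that both additions condition on an event after randomization, so they should be labeled as supporting the by-arm comparison and not replacing it.

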### 9.2 Methods and Timing for Assessing, Recording, and Analyzing Safety Parameters

#### 9.2.1 Adverse Events

**Adverse Event (AE):** ICH E6 defines an AE as any untoward medical occurrence in a patient or clinical investigation subject administered a pharmaceutical product regardless of its causal relationship to the study treatment. An AE can therefore be any unfavorable and unintended sign (including an abnormal laboratory finding), symptom, or disease temporally associated with the use of medicinal (investigational) product. The occurrence of an AE may come to the attention of study personnel during study visits and interviews of a study recipient presenting for medical care, or upon review by a study monitor. FDA defines an AE as any untoward medical occurrence associated with the use of a drug in humans, whether or not considered drug related.

AEs not meeting the protocol-defined criteria for SAEs will be captured on the appropriate electronic case report form (eCRF). Information to be collected for non-serious AEs includes event description, date of onset, licensed study physician's assessment of severity and relationship to study product and alternate etiology (if not related to study product) (assessed only by those with the training and authority to make a diagnosis and listed on the Form FDA 1572 as the site principal investigator or sub-investigator), date of resolution of the event, seriousness and outcome. AEs occurring during the collection and reporting period will be documented appropriately regardless of their relationship to the study product. All recorded AEs will be followed to adequate resolution. Any medical condition that is present at the time that the subject is screened will be considered as baseline and not reported as an AE. However, if the severity of any pre-existing medical condition increases at any time during the study, it will be recorded as an AE. AEs must be graded for severity and assessed for relationship to study product (see definitions below). Adverse events characterized as intermittent require

documentation of onset and duration of each episode. The start and stop date of each reported AE will be recorded on the appropriate eCRF. Bacterial resistance will be reported based on the report from the laboratory.

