**Severity of Event:** AEs will be assessed by a licensed study physician listed on the Form FDA 1572 as the site principal investigator or appropriate sub-investigator. The severity of non-serious AEs will be assessed according to the scale below:

- **Mild:** events require minimal or no treatment and do not interfere with the subject's daily activities.
- **Moderate:** events result in a low level of inconvenience or concern with the therapeutic measures. Moderate events may cause some interference with functioning.
- **Severe:** events interrupt a subject's usual daily activity and may require systemic drug therapy or other treatment. Severe events are usually incapacitating.

Examples of the types of non-serious AEs that will be collected (contained within the heavy lines) and AEs that will not be collected (gray font and marked by an asterisk) are shown in the Table below.

Table 4. Procedure for Recording of Non-Serious Adverse Events

Non-Serious Adverse Events			
	Mild	Moderate	Severe
Rash	*Localized	Generalized and moderate	Generalized and severe (e.g., severe urticaria; serum sickness; Stevens-Johnson Syndrome)
Diarrhea	*Loose stools	3 or more watery stools in 1 day or 2 watery stool daily for at least 2 days (i.e., PDD)	Diarrhea requiring rehydration therapy and is incapacitating
All other Adverse Events	*Requires minimal or no treatment and does not interfere with daily activities	*Requires some treatment and may interfere with daily activities	Requires systemic drug therapy and is clearly incapacitating
Bacterial resistance	N/A	N/A	All bacterial resistance will be collected

\*AEs that will not be collected

**Relationship to Study Products:** The study physician's assessment of an AE's relationship to the study product is required prior to unblinding and is part of the documentation process, but it

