#### **9.2.4 Procedures to be Followed in the Event of Abnormal Laboratory Test Values or Abnormal Clinical Findings**

NP specimens will be obtained for culture at baseline and follow-up for the identification of *S. pneumoniae*, *H. influenzae*, and *M. catarrhalis*. Detection of *S. pneumoniae*, *H. influenzae*, and *M. catarrhalis* in the nasopharynx will be considered a normal finding.

Study product may need to be discontinued in subjects with a clinical adverse event, laboratory abnormality, intercurrent illness, or other medical condition such that continuation of study product would not be in their best interest. Randomization codes will not be broken at any time in the event of treatment failure unless deemed necessary for medical /emergency/safety reasons. These subjects will be asked to continue to record their symptoms on the PRSS on a daily basis and to return to the clinic for a routine end-of-study follow-up visit to be held once during Days 12 to 18.

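### Section 11.10.2 compares study-product stops due to adverse events, but 9.1 and Table 4 leave most non-severe events uncollected, with no exception for an event that causes a stop (minor, cheap to fix)

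*Combined protocol and SAP*

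**What the plan says.** **The planned analysis.** Section 11.10.2 states that "study medication discontinuation due to adverse events will also be compared using" Fisher's exact test. It also promises data listings and narratives for patients who stop treatment because of an adverse event.

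**When a stop may happen.** Section 9.2.4 sets no severity threshold: "Study product may need to be discontinued in subjects with a clinical adverse event, laboratory abnormality, intercurrent illness, or other medical condition". Section 6.3 also foresees stops because of adverse events, again without a grade, and says that these children will receive a replacement antibiotic.

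**What is collected.** Because the product is already licensed for sinusitis, 9.1 restricts collection: "we will only track 1) common or important adverse events linked with the study product (PDD, generalized rash"), then severe events, defined as "severe adverse event (AEs which require more than minimal medical intervention, Table 4, below"), then serious events. Bacterial resistance is tracked as well. Section 9.2.1 introduces Table 4 with the statement that "AEs that will not be collected (gray font and marked by an asterisk) are shown in the Table below". The asterisked cells are localized rash, loose stools, and both the mild and the moderate grade of all other adverse events. The moderate cell of that last row reads "Requires some treatment and may interfere with daily activities".

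**Which fields are recorded.** Section 9.2.1 says "Information to be collected for non-serious AEs includes event description, date of onset", followed by severity, relationship and alternate etiology, and ends with "date of resolution of the event, seriousness and outcome". Action taken with study product is not among the fields.

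**Listed grounds for stopping.** Section 5.3.2 names two: parent or guardian request, and failure to complete diaries in the first four days.

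**The concern.** A count of stops due to adverse events needs two linked facts for each child: that study product was stopped, and which event caused it. The collection rule removes the second fact for a class of events that the protocol itself regards as drug effects. Section 2.3.1 names vomiting, nausea, diaper rash and abdominal pain, and a parent could plausibly stop a twice-daily suspension for any of these without the event being severe.

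At stake are the completeness of one tolerability comparison and the ability to write the promised narratives. The trial asks which children benefit enough from an antibiotic to justify giving it, and stopping because of side effects is one of the plainer measures on the other side of that balance.

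**Working it through.** The documents give no stop rate, power or sample size for this comparison, so there is no planned figure to reproduce. The check is mainly a reading of the sections against each other.

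**1. Size of the exclusion in Table 4.** There are 4 rows × 3 grades = 12 cells. Two are not applicable (bacterial resistance, mild and moderate), leaving 12 − 2 = 10. Four of these are asterisked: localized rash, loose stools, all other mild, all other moderate. In the row for all other events, 2 of 3 grades are not collected.

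**2. Which known effects fall there.** Section 2.3.1 names six bodily side effects: diarrhea, vomiting, nausea, diaper rash, abdominal pain and anaphylaxis. Four of the six (vomiting, nausea, diaper rash, abdominal pain) have no AE record when non-severe. This counts types, not frequency. Section 2.3.1 puts diarrhea at one third to one half of children and calls these four infrequent.

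**3. Does the intervention wording in 9.1 rescue them?** Section 9.1 attaches the phrase about more than minimal medical intervention to severe events and refers to Table 4. There, an event needing some treatment is moderate and asterisked. The more direct reading is that the phrase does not widen collection, although a replacement antibiotic could be argued to meet it.

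**4. Where a stop could still leave a trace.**

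| Source | What it gives | What is not stated |
|---|---|---|
| 11.6.3 | Withdrawal reasons by arm | Whether a child who stops product but stays in follow-up counts as withdrawn |
| 7.5 | Visit if a parent is concerned; AE monitoring may be done | Recording of an excluded event |
| 6.3, 6.6, 15.2 | Replacement antibiotic; records on why it was given, if needed | A link from the stop to the event |
| 7.3 | Daily questions on doses and adverse events | Reason for missed doses |
| 7.4 | Adverse events asked about at the final visit | Recording of an excluded event |

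Each source may reveal the stop. None is said to tie it to its event.

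**5. Illustration only.** Assume stop rates of about 6% and 2% with 344 children per arm (the planned number): 0.06 × 344 = 20.6, taken as 21, and 0.02 × 344 = 6.9, taken as 7. Assume also that a stop with no AE record leaves the Fisher numerator. The documents support none of these assumptions. Counts are rounded, for example 21 × 0.75 = 15.75, taken as 16. The difference is (drug count − placebo count)/344, and p is from the two-sided Fisher exact test.

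| Assumed unrecorded share | Drug vs placebo | Difference (points) | p |
|---|---|---|---|
| None | 21 vs 7 | 4.07 | 0.011 |
| 10% in both arms | 19 vs 6 | 3.78 | 0.013 |
| 25% in both arms | 16 vs 5 | 3.20 | 0.024 |
| 25% in drug arm only | 16 vs 7 | 2.62 | 0.088 |
| 25% in placebo arm only | 21 vs 5 | 4.65 | 0.002 |

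Exact Fisher power at 6% vs 2% (two-sided 0.05) is 0.73 with full capture and 0.58 with 25% missed in both arms. The table shows that the reported difference could move either way. It does not estimate how far it would move.

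**The case against.** The strongest reply is that discontinuation due to an adverse event is a disposition variable and can be counted without an AE form. Section 11.6.3 tabulates withdrawal reasons by arm, and 5.3.2, under a heading about withdrawal, opens by speaking of discontinuation from study product, so a stop reason is arguably required already. By promising listings and narratives, 11.10.2 implies that stop and cause will be captured. Followed as written, 6.3 gives every child stopped for an adverse event a replacement antibiotic, and receipt of one on Days 1 to 11 is itself a secondary outcome. Table 4 is introduced as examples, 9.2.1 asks for reporting when it is doubtful whether an observation is an adverse event, and the eCRF and Manual of Procedures, which are not available here, may contain a stop-reason field.

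Much of this stands. It makes the loss partial and defeats the stronger inference that stops for non-severe events disappear from the Fisher comparison: no text says that a stop without an AE form is left out of the count.

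It does not remove the gap. The two reasons in 5.3.2 do not include an adverse event, so a tabulation built on them would show such a stop as parent request. Section 9.2.4 keeps children who stop product in follow-up, which leaves it unclear whether 11.6.3 counts them. The doubt clause concerns whether something is an adverse event, not whether an acknowledged event of an excluded type is collected. A parent who stops at home and receives no replacement antibiotic departs from 6.3, but then only missed diary doses and answers to the adverse-event questions remain. Restricted collection for a licensed product is a reasoned choice; the difficulty is only that it was not reconciled with the planned comparison.

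**Conclusion.** The point holds as a minor one. A stated collection rule conflicts with a planned safety analysis: some stops due to adverse events would have no AE record of the event that caused them, and the protocol names no other required record linking the two.

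The effect is confined to a tertiary safety comparison and its listings and narratives. It is probably modest, because protocol-defined diarrhea and generalized rash are collected and the other named non-severe effects are described as infrequent.

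A reader might infer from the illustration that a real difference would be lost, or that the comparison is biased in favor of the drug. The documents support neither. The stop rates, the unrecorded shares, and the removal of unrecorded stops from the numerator are all assumptions, and the direction changes with the arm in which records are missing. The conclusion rests on the protocol text alone; a stop-reason field in the eCRF or Manual of Procedures would reduce the problem to one of wording.

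**What to change.** In 9.1 and as a footnote to Table 4, state that any adverse event leading to discontinuation of study product is recorded on the AE eCRF whatever its type or grade, with the stop date and reason. In 11.10.2, define discontinuation due to adverse events from that record. Restricted collection of all other mild and moderate events stays as it is. Adding adverse event to the grounds in 5.3.2 is optional tidying, since 9.2.4 already allows it.

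The cost is one sentence in each place and an action-taken item, with stop date and reason, on the AE eCRF. No new visit or contact is needed, because the diary and the final visit already ask about adverse events and the diary records doses. Sample size, alpha and the primary analysis are unchanged. The downside is a few more AE forms (28 × 0.10 = 2.8 to 28 × 0.25 = 7.0 over both arms, if 10% to 25% of an assumed 28 stops are of an excluded type) and possibly a slightly higher reported discontinuation rate.
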